Cover Page

Study Title:

Prostatic Artery Embolization (PAE) for Treatment of Signs and
Symptoms of Benign Prostatic Hyperplasia (BPH)

NCT:

NCT03052049

Last reviewed by Northwestern University IRB 11/19/2021

Protocol version 12.3.2019

Protocol version 12.3.2019

Prostatic Artery Embolization (PAE) for Treatment of Signs and Symptoms of Benign Prostatic Hyperplasia (BPH)

Title	Prostatic Artery Embolization (PAE) for Treatment of Signs and symptoms of Benign Prostatic Hyperplasia (BPH)
Short Title	PAE for BPH
Protocol Number	V 12.3.19
Phase	Pilot study
Methodology	Open labeled, non-randomized feasibility study
Study Duration	We estimate it will take approximately 2 years to fully enroll and complete the study.
Study Center(s)	Single Center, Northwestern: (Northwestern University, Northwestern Memorial Hospital and Northwestern Memorial Faculty Foundation)
Objectives	Primary Objective: Evaluate the safety of PAE for the treatment of lower urinary tract symptoms (LUTS) attributed to BPH.
Number of Subjects	30
Diagnosis and Main Inclusion Criteria	Subjects with LUTS secondary to BPH refractory to/contraindicated for medical treatment
Study Product(s)	BeadBlock® Embolic Beads, BTG International, given intra-procedurally
Duration of administration	Dose given one-time during interventional radiology PAE procedure, given by and at the discretion of the interventional radiologist PI or Subl's
Statistical Methodology	Descriptive Statistics will be employed.

STUDY OBJECTIVES

Primary Objectives

Endpoint #1: Patient safety

The Primary Objective of this pilot study is to evaluate the safety of PAE for the treatment of LUTS attributed to BPH. Primary Safety Endpoints include:

1. A reduced incidence and severity of adverse events compared with historical TURP morbidity rates. These include genitourinary events (i.e., events associated with the urinary tract and/or the surrounding genital region)
2. Damage to the bladder floor, trigone, sphincters, and rectum
3. Incontinence as defined by International Continence Society (ICS) male IS score of at least +6 from baseline.
4. Infections
5. Secondary surgical interventions
6. All transient post-procedure events (i.e. *catheter dwelling time*)
7. Deaths

Endpoint #2: Objective clinical endpoints (measured at baseline, 4 weeks, 12 weeks, 6 and 12 months)

1. Change in International Prostate Symptom Score (IPSS)
2. Change in QoL bother question
3. Change in BPH impact index
4. Change in Qmax (*peak and total void volume at each followup visit*)
5. Change in Post Void Residual (PVR) Volumes: Measure PVR at each follow-up visit to monitor impairment or improvement of bladder emptying due to the treatment or disease progression
6. Change in Detrusor Muscle Pressure (Pdet) at Peak Urine Flow (Qmax)
7. Change in International Index of Erectile Function (IIEF- EF) domain
8. Change in Male Sexual Health Questionnaire (MSHQ)
9. Change in Prostate Volume
10. Cystoscopic appearance of the prostatic urethra

Endpoints:

Preliminary Safety (Primary Endpoints) will be assessed during treatment and at post-treatment intervals of 1, 3, 6 and 12 months. Preliminary effectiveness (Secondary Endpoint) will be evaluated based on International Prostate System Score (IPSS) and cystoscopic visualization of the subject's urethra, prostate and bladder based on the timeline listed in the protocol.

Study Design

This pilot study will be a single center, open labeled, non-randomized feasibility study to evaluate the initial safety of the PAE for the treatment of symptomatic BOO. 30 adult male subjects will be enrolled in this study.

Statistical Analysis

General considerations: continuous variables will be summarized as n, mean, standard deviation, median, minimum and maximum. Categorical variables will be summarized as the number and percentage of patients in each category.

This is a single center pilot proof of concept study aiming to evaluate the safety, efficacy, and tolerability of PAE for the treatment of signs and symptoms BPH. A small number of subjects will be recruited for this purpose (30 subjects). We estimate it will take approximately 3 years to recruit, treat, and complete follow up on 30 subjects.

No large randomized studies using PAE to treat BPH have been done to date. The sample size has been chosen to evaluate PAE using a US population. The results of the study will provide critical preliminary data to later guide in powering a more statistically robust, and larger randomized controlled trial in the future.

Sample size justification

To detect a statistically significant reduction from baseline in IPSS at 12 weeks, a sample size of 30 patients is computed based on the following assumptions:

- 85% power
- 2-sided alpha of 0.05
- Mean reduction of 5 points
- SD of reduction of 8 points The sample size of 28 is rounded up to 30 patients to take account of approximately 15% of patients who drop-out of the study.

Planned analysis of clinical endpoints

Change in IPSS, QoL bother question, BPH impact index and Qmax will be assessed using a one- sample t-test. A log transformation may be applied if required to adjust for skewed data. In addition a non-parametric Wilcoxon test will also be performed.

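### Primary safety item 1 is worded as a favourable result against historical TURP, a comparison that this uncontrolled 30-patient pilot does not define; it should be worded neutrally

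*Combined protocol and SAP*

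**What the plan says.** Under Study Objectives, Endpoint #1 (Patient safety), the stated aim is neutral: to assess how safe PAE is. Seven primary safety items follow. The first is "A reduced incidence and severity of adverse events compared with historical TURP morbidity rates", and the text adds that genitourinary events are included. The other six (organ damage, incontinence by a score threshold, infections, further surgery, transient events, deaths) name things to be recorded and carry no comparator.

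The Study Design section states: "This pilot study will be a single center, open labeled, non-randomized feasibility study to evaluate the initial safety of the PAE". Enrolment is 30 men. On timing, the Endpoints section says: "Preliminary Safety (Primary Endpoints) will be assessed during treatment and at post-treatment intervals of 1, 3, 6 and 12 months".

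On analysis, the synopsis says "Descriptive Statistics will be employed". The general considerations under Statistical Analysis say "Categorical variables will be summarized as the number and percentage of patients in each category", and this is the only summary that applies to adverse events. Tests are reserved for efficacy: "Change in IPSS, QoL bother question, BPH impact index and Qmax will be assessed" with a one-sample t-test, supplemented by a Wilcoxon test. The same Statistical Analysis section says that the results "will provide critical preliminary data to later guide in powering a more statistically robust, and larger randomized controlled trial".

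**The concern.** An endpoint should name what is measured. Item 1 instead names the answer hoped for, and does so relative to a treatment that nobody in the study receives. To decide whether it was met, a reader would need a TURP rate, its source, the patients it came from, the event definitions and severity scale behind it, the follow-up window and a rule for 'reduced'. The available text gives none of these.

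The risk lies in the report. Counts and percentages from 30 patients could be set beside a TURP figure chosen later, and the first-listed primary safety item declared met. Differences in patients, event definitions, ascertainment or length of follow-up could produce such a contrast without any difference in safety. A comparative statement of that kind also does little for the plan's own purpose, which is to inform a later randomized trial. An event rate with its uncertainty does serve that purpose.

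**Working it through.** **1. The plan's own figure.** The only computed figure is the sample size, and it concerns IPSS at 12 weeks. Inputs from Sample size justification: mean reduction 5, SD 8, two-sided alpha 0.05, power 85%, dropout about 15%. A one-sample t-test (noncentral t) needs n = 25 (power 85.03%; n = 24 gives 83.4%). Allowing for dropout, 25/(1 − 0.15) = 29.4, rounded up to 30. The total of 30 reproduces, but no adverse-event rate enters it.

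**2. What item 1 needs, against what the text gives.**

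| Needed to judge 'reduced versus TURP' | In the available text |
|---|---|
| TURP rate and its source | Not given |
| Comparable patients | No concurrent control; no matching described |
| Event definitions and severity scale | Genitourinary events are included; no scale |
| Matching time window | PAE visits to 12 months; none for TURP |
| Rule for 'reduced' | Not given |
| Analysis | Number and percentage |

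**3. Precision with n = 30.** Exact (Clopper-Pearson) two-sided 95% limits for x events are: lower = Beta quantile 0.025 with parameters (x, n − x + 1); upper = Beta quantile 0.975 with parameters (x + 1, n − x). For x = 0 the upper limit is 1 − 0.025^(1/30) = 11.6%. The one-sided 95% limit is 1 − 0.05^(1/30) = 9.5%.

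| Events | Rate | Exact 95% interval |
|---|---|---|
| 0/30 | 0% | 0 to 11.6% |
| 3/30 | 10.0% | 2.1 to 26.5% |
| 6/30 | 20.0% | 7.7 to 38.6% |
| 9/30 | 30.0% | 14.7 to 49.4% |

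Even a record with no events would not show a reduction against a benchmark below 11.6% (two-sided 95% limit) or 9.5% (one-sided).

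**4. What 30 patients could detect.** The documents give no benchmark, so a range of rates p0 is assumed, each halved under PAE. The exact one-sided test rejects when X ≤ c, where c is the largest value with P(X ≤ c | p0) ≤ alpha. Power is P(X ≤ c | p0/2). For example, at p0 = 10% and alpha 0.05, 0.90^30 = 0.042, so c = 0 and power = 0.95^30 = 21%.

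| Assumed TURP rate, halved under PAE | Power, one-sided 0.05 | Power, one-sided 0.025 |
|---|---|---|
| 5% | rejection impossible | rejection impossible |
| 10% | 21% | rejection impossible |
| 20% | 41% | 18% |
| 30% | 52% | 32% |
| 40% | 76% | 61% |
| 50% | 89% | 80% |

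Sample size is therefore a firm limit at low benchmarks but not at high ones. The absence of a control and of any definition of the comparison applies at every benchmark.

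**The case against.** The strongest reply is that this is a descriptive pilot and the text around item 1 already says so. The objective is neutral, safety is called preliminary, the method is descriptive, and robust inference is left to a later trial. On that view item 1 merely names the background against which the counts will be read. Much of this stands: a descriptive pilot needs no test of adverse events, and no section plans a formal comparison with TURP. But a descriptive plan is a reason to word the endpoint descriptively, and item 1 is the only one of the seven that is not.

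A second reply is that the TURP rates may sit in text that is not available. The Endpoints section points to a timeline in the protocol that does not appear, so this is possible. It limits confidence in what is absent, but not in the wording. A rate given elsewhere would still leave a favourable result listed as an endpoint of an uncontrolled study.

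Three stronger readings are tempting and are not supported:

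- A reader might infer that 30 patients can never show a reduction. At an assumed benchmark of 50%, halved, power is 89%.
- A reader might infer that item 1 would be met about half the time by chance. That presumes 'reduced' means an observed percentage below a benchmark, a rule the documents do not contain. An estimate falls below its true value about half the time at almost any sample size, so this says little about this trial.
- A reader might infer that sizing the study on IPSS is itself an error. In a descriptive safety pilot it is not.

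**Conclusion.** The point holds and is confined to the wording and reporting of one primary safety item. The main limit is design: any 'reduced versus TURP' conclusion would compare 30 uncontrolled patients with unspecified historical ones, and a statistically detectable difference would not cure that. Limited precision adds to it, most of all at benchmarks below about 10% to 12%.

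Confidence is high for the wording. For the missing rate, source and rule it is conditional on the available text being complete on this point. The intervals use 30 treated patients, each counted once per event category. The power figures rest on assumed TURP rates and an assumed halving, and serve only to show where sample size matters. The item should be corrected because the change costs little and prevents an unsupported safety claim. Nothing here questions the study's size or conduct.

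**What to change.** Reword item 1 as: the incidence and severity of adverse events, including genitourinary events, through 12 months. Name the severity scale. Report n/N of treated patients with an exact 95% confidence interval, tabulated by severity.

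Show beside it the number followed to 12 months, and state that n counts observed events only, so the rate is a minimum where patients left early. The plan expects about 15% dropout, and 0.15 × 30 = 4.5, or four to five patients.

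If TURP is to stay in view, show published rates with their source, event definitions, severity scale and time window. Label them descriptive context and make no confirmatory claim of a reduction.

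The cost is one line in the protocol and a few added entries in the adverse event table and its source notes, with no extra patients or visits. The downside is a weaker headline claim.

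### The primary safety endpoint is a comparison with historical TURP rates, but the plan reports event rates only as number and percentage, with no confidence interval.

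*Combined protocol and SAP*

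**What the plan says.** All references are to the combined protocol and SAP.

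- **Primary Objectives, Endpoint #1.** "The Primary Objective of this pilot study is to evaluate the safety of PAE for the treatment of LUTS attributed to BPH". The first listed safety endpoint is "A reduced incidence and severity of adverse events compared with historical TURP morbidity rates". No numerical TURP rate is given, and nothing says how the comparison will be made.
- **Synopsis, Statistical Methodology.** "Descriptive Statistics will be employed".
- **Statistical Analysis, General considerations.** For measurements, "continuous variables will be summarized as n, mean, standard deviation, median, minimum and maximum". For events, "Categorical variables will be summarized as the number and percentage of patients in each category".
- **Planned analysis of clinical endpoints.** One-sample t-tests and Wilcoxon tests are planned for change in IPSS, the QoL bother question, the BPH impact index and Qmax. No safety outcome is included, and no interval is named.
- **Statistical Analysis, on purpose.** The study aims at safety, efficacy and tolerability. Its results are also to provide "critical preliminary data to later guide in powering a more statistically robust, and larger randomized controlled trial in the future".

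**The concern.** Saying that a rate is lower than a historical one needs two things: the historical rate, and some statement of how far the observed rate could be from the truth. The plan provides neither for its primary endpoint. The efficacy endpoints, which come second to safety, do get tests that allow for sampling error.

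Followed as written, the report would set a count and percentage from 30 men beside a TURP figure, and a smaller percentage could be described as a reduction. With so few patients, a percentage of 0% or 3% looks reassuring while remaining compatible with rates several times higher. What is at stake is whether the trial's main safety conclusion is supported by its data.

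**Working it through.** **Inputs from the document.** 30 subjects, 85% power, "2-sided alpha of 0.05", mean IPSS reduction 5, SD of reduction 8, about 15% drop-out. The historical TURP rate is not given.

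**1. The plan's own figure.** Sample size justification arrives at 30 patients from the IPSS change.
- Normal approximation: n = (8 × (1.960 + 1.036) / 5)² = 22.98, so 23. Allowing for 15% drop-out, 23 / 0.85 = 27.1, so 28.
- Exact t-test: n = 25 gives power 0.850. Allowing for drop-out, 25 / 0.85 = 29.4, so 30.

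The total of 30 is therefore reproduced. It was derived for an efficacy mean, not for the precision of any safety rate. After 15% drop-out, 30 × 0.85 = 25.5, so about 25 are evaluable at later visits.

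**2. Precision of a safety proportion.** The Clopper-Pearson 95% limits for x events in n patients are the 0.025 quantile of Beta(x, n − x + 1) and the 0.975 quantile of Beta(x + 1, n − x). For x = 0 the lower limit is 0 and the upper limit is 1 − 0.025^(1/n). At n = 30 this is 1 − 0.025^(1/30) = 0.116.

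| Events / n | Observed | Exact 95% CI |
|---|---|---|
| 0/30 | 0% | 0 to 11.6% |
| 1/30 | 3.3% | 0.1% to 17.2% |
| 2/30 | 6.7% | 0.8% to 22.1% |
| 3/30 | 10.0% | 2.1% to 26.5% |
| 5/30 | 16.7% | 5.6% to 34.7% |
| 0/25 | 0% | 0 to 13.7% |
| 3/25 | 12.0% | 2.5% to 31.2% |

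The upper limit shows what the comparison can bear. If the TURP rate is treated as a fixed number, the interval lies wholly below it only when that number exceeds 11.6% with no events in 30, 17.2% with one, or 26.5% with three. Since the document gives no TURP rate, these thresholds stand in for it.

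**3. Precision of a mean change.** The half-width is t(0.975, n − 1) × SD / √n. At SD 8 it is 3.30 points with n = 25 and 2.99 points with n = 30. The planned t-test allows for this error, but the listed summaries do not display it.

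**4. Precision of the SD.** The limits are SD × √(df / χ² quantile). At an observed SD of 8 and n = 25 (df = 24), they are 6.25 and 11.13. At n = 30 (df = 29), they are 6.37 and 10.75. Here 8 is the planning value, used for illustration, and the formula assumes normally distributed changes.

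**The case against.** The strongest reply is that no information is lost. The plan reports n, mean, SD and counts, and from these any reader can compute every interval above. That is largely true, and for the SD it reduces the matter to presentation. It does not settle the safety point. The comparison with TURP is this trial's own primary endpoint, so the plan should say how its report will judge it and not leave that to the reader.

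It may also be said that a pilot described as descriptive needs no inference. A purely descriptive safety table would indeed be acceptable with counts alone. But the endpoint is worded as a reduction against an external rate, which is more than description.

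A reader might go further and infer that the study exists to size a randomised trial, and that its SD and event rates will be carried into that trial as if known. The documents do not support this. Guiding a later trial is one stated use, the primary objective is safety, and nothing describes how the later trial would be sized. Nor is it right that the plan has no inference at all, since the t-tests and Wilcoxon tests allow for sampling error in four efficacy changes. How a later trial should allow for an uncertain SD belongs to that trial's protocol.

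**Conclusion.** The concern holds for primary safety. The plan sets a comparison with historical TURP rates and gives it only a number and percentage. With 30 patients the exact 95% upper limit is 11.6% after no events, 17.2% after one and 26.5% after three, so a lower observed percentage alone cannot establish reduced incidence.

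These figures assume that all 30 patients contribute to the safety denominator and that limits are two-sided at 95%. With 25 patients the limits are wider. They also treat the historical rate as known exactly, and allowing for its own error would make the comparison harder.

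The missing intervals for mean changes are a lesser reporting gap, because tests are planned for four of those endpoints. An interval for the SD is optional. None of this makes the stated total of 30 wrong. The change should be made, but it is a correction to the analysis wording, not a flaw in the design.

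**What to change.** Amend General considerations along these lines:

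- Each safety proportion will be given as number, denominator and percentage with an exact (Clopper-Pearson) 95% confidence interval.
- Comparison of adverse-event incidence with the historical TURP rate will be judged against that interval, not against the observed percentage alone. For this to be applied, the historical rate and its source must be written into the plan.
- Mean changes from baseline will be given with 95% confidence intervals.
- Optionally, the SD of the 12-week IPSS change will be given with its 95% confidence interval, since later trial powering is a named use.

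The cost is a few lines of wording and code, plus stating the comparator rate. No extra patients, visits or data are needed, and the sample size is unchanged. The one drawback is that the safety results will look less favourable than bare percentages.

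### Does the efficacy analysis need changing because cystoscopy has no stated categories and the 12-week IPSS test is not named as the lead?

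*Combined protocol and SAP*

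**What the plan says.** Efficacy outcomes appear in four places in the combined protocol and SAP.

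- **Endpoint #2**, under the Primary Objectives heading, lists ten items with a baseline and four later visits. Item 10 is "Cystoscopic appearance of the prostatic urethra".
- **The Endpoints paragraph** calls safety primary and then states: "Preliminary effectiveness (Secondary Endpoint) will be evaluated based on International Prostate System Score (IPSS) and cystoscopic visualization". The structures to be viewed, and the timing, are given as "urethra, prostate and bladder based on the timeline listed in the protocol".
- **Sample size justification** sets its purpose as "To detect a statistically significant reduction from baseline in IPSS at 12 weeks", with 85% power, two-sided alpha 0.05, a mean reduction of 5 points and an SD of 8.
- **Planned analysis of clinical endpoints** states: "Change in IPSS, QoL bother question, BPH impact index and Qmax will be assessed using a one- sample t-test". It continues: "A log transformation may be applied if required to adjust for skewed data". It then says: "In addition a non-parametric Wilcoxon test will also be performed".

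Under General considerations, the rule that would reach a graded finding is "Categorical variables will be summarized as the number and percentage of patients in each category". The synopsis describes the statistical methodology as descriptive.

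**The concern.** Only IPSS is common to all four places. Cystoscopy is one of the two named bases of effectiveness, yet the analysis section omits it. The general rule for categorical data needs categories, and the supplied text gives none. In an open-label study, grading criteria settled late could be shaped by what has been seen. The anatomical scope also differs: item 10 names the prostatic urethra, while the Endpoints paragraph adds the prostate and bladder.

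The tests look loosely specified too. Four variables at four post-baseline visits allow 16 t-tests, each with a Wilcoxon companion. No lead is named where the tests are described. The log transformation has no trigger, and it cannot be applied to changes that are zero or negative. Finally, Endpoint #2 sits under a primary heading while effectiveness is called secondary.

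If these points left the main efficacy result open to choice after the data were seen, the IPSS claim would be less secure and the cystoscopy report hard to interpret.

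**Working it through.** **1. The plan's own sample size.** The inputs are those in Sample size justification, so the standardised effect is d = 5/8 = 0.625.

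- Normal approximation: n = (z₀.₉₇₅ + z₀.₈₅)² × (8/5)² = 22.98, so 23.
- One-sample t-test (noncentral t): the smallest n with power of at least 0.85 is 25 (power 0.8503).
- Allowing for 15% dropout: 25 / 0.85 = 29.4, so 30, which is the stated N. With all 30 evaluable, power is 0.911.

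The stated N therefore corresponds to one two-sided t-test of the 12-week IPSS change at 0.05. (The intermediate figure of 28 is not the evaluable number by either method. That is a separate matter and does not affect this point.)

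**2. How much the choice between t and Wilcoxon matters.** Simulation of 400,000 trials with normally distributed changes and exact signed-rank critical values (exact size 0.0483 at n = 25, 0.0497 at n = 30):

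| Completers | t-test | Wilcoxon | Either | Both | Disagree |
|---|---|---|---|---|---|
| 25 | 0.850 | 0.831 | 0.861 | 0.821 | 0.040 |
| 30 | 0.912 | 0.900 | 0.920 | 0.892 | 0.028 |

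The last column is either minus both: 0.861 − 0.821 = 0.040 and 0.920 − 0.892 = 0.028. With no true change, at least one of the two tests is significant in 0.058 of trials at both sizes. The most favourable choice therefore costs about 0.8 percentage points of type I error.

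**3. Multiplicity with no lead test.** If the tests were independent, the chance of at least one false positive would be 1 − 0.95⁴ = 0.19 for four tests and 1 − 0.95¹⁶ = 0.56 for sixteen. Independence is an assumption. The outcomes and visits are correlated, so these figures illustrate the upper end. They would matter only if any significant result counted as success, and the plan does not say that.

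**4. Coverage of the ten Endpoint #2 items.** Items 1–4 have a named test. Items 5–9 (residual volume, detrusor pressure, the two sexual function scores, prostate volume) are numeric and fall under the general summary for continuous variables. Item 10, cystoscopy, is the only one with no named test and no stated scale: 4 + 5 + 1 = 10.

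**5. The text set side by side.**

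- *Lead test and visit:* the only efficacy comparison given an effect size, alpha and visit is the 12-week IPSS change. The visits for the other outcomes are in the Endpoint #2 heading.
- *Wilcoxon:* it follows the t-test and is introduced as an addition, which reads naturally as supportive.
- *Other tested variables:* QoL bother, BPH impact index and Qmax are items 2–4 of Endpoint #2, so they have a stated place. Only a ranking is absent.
- *Primary or secondary:* the synopsis and Endpoint #1 both give safety as the primary objective, and the Endpoints paragraph labels effectiveness secondary. The heading over Endpoint #2 is a clerical slip.
- *Cystoscopic scope:* the wider phrase can describe what is inspected and item 10 what is reported as a clinical outcome. Endpoint #1 also counts damage to the bladder floor and trigone as a safety outcome, which would explain the wider view.
- *Log transformation:* it is optional. An analyst who needed it would apply it to the raw baseline and follow-up values, because it is undefined for zero or negative changes.

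**The case for a change.** The strongest case for a change is cystoscopy. The lead test can be inferred, but cystoscopic categories cannot. As written, one of the two named bases of effectiveness cannot be tabulated, and nothing in the text prevents the criteria being settled after findings are known. Calling the study descriptive does not answer this, because a descriptive count itself needs categories. The plan also intends the results to guide a later randomised trial, so readers should know which result leads. Writing these things down would cost a paragraph, with no loss of power and no change in N.

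Part of this stands: the supplied text has no cystoscopic categories, and listing them before follow-up findings are graded would be good practice. But nothing in the documents shows that grading would be left until after treatment. Categories could be on a data form, or appearance could be reported narratively. The text also points to a timeline that is not among the supplied pages. Any bias is therefore possible rather than shown, and no figure can be put on it. Adding the missing wording would record what a reader already infers, plus a list for the investigators to choose. It would not correct a rule that gives a wrong result or replace a method with a better one.

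**Conclusion.** No change to the plan follows. This is a gap in documentation, plus one misplaced heading, that the investigators and the analyst can be expected to fill sensibly. The 12-week IPSS t-test is identifiable as the lead from the sample size section. Its power is 85.0% with 25 completers and 91.1% with 30, and N = 30 stands. Using the Wilcoxon instead would lower power by about 2 percentage points at 25 completers (85.0% − 83.1% = 1.9). Taking whichever test is significant would raise the type I error to about 5.8%. The one item without a ready summary is cystoscopy, one of ten Endpoint #2 items and part of a secondary endpoint. Its absence from the test list does not touch the IPSS result or the primary safety assessment.

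The figures assume the plan's effect and SD, normally distributed changes, and about 15% dropout (30 × 0.85 = 25.5, taken as 25). The conclusion also assumes that the added Wilcoxon test is read as supportive and that cystoscopic findings are reported descriptively.

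### With about 15% drop-out expected and no missing-data method stated, the 12-week IPSS test by default omits men without a 12-week value; response-related drop-out would then overstate the mean reduction passed to the next trial

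*Combined protocol and SAP*

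**What the plan says.** Planned analysis of clinical endpoints contains the whole inferential method for efficacy: change in IPSS, QoL bother, BPH impact index and "Qmax will be assessed using a one- sample t-test". A log transformation is allowed for skewed data, and "In addition a non-parametric Wilcoxon test will also be performed".

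Sample size justification ties the study size to one analysis, "To detect a statistically significant reduction from baseline in IPSS at 12 weeks", with 85% power, "2-sided alpha of 0.05", "Mean reduction of 5 points" and an SD of 8. It rounds 28 up to 30 to allow for "approximately 15% of patients who drop-out of the study".

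Endpoint #2 under Study Objectives lists "Objective clinical endpoints (measured at baseline, 4 weeks, 12 weeks, 6 and 12 months", so four follow-up values per man are scheduled.

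The documents name no analysis set, missing-data rule, imputation, longitudinal model or sensitivity analysis. The Endpoints section classes preliminary effectiveness as secondary. Statistical Analysis says that the results are to help power a larger randomized trial.

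**The concern.** A one-sample t-test or Wilcoxon test on change at 12 weeks needs both a baseline and a 12-week value. A man who attends at 4 weeks and then leaves contributes nothing to it, although his 4-week change has been recorded. Enlarging the sample restores power but does not make the remaining men representative.

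The test is unbiased if leaving is unrelated to response. If men with little early benefit leave more often, those who remain have a larger mean change and a smaller spread than all treated men. In a single-arm study no control group offsets this. At stake are the mean and SD of 12-week IPSS change, the one quantity on which the study is sized and a natural input to the later trial.

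**Working it through.** **1. The plan's sample size.** Inputs from Sample size justification: mean 5, SD 8, two-sided alpha 0.05, power 85%, drop-out 15%. The noncentral-t calculation for a one-sample test gives n = 25 (power 85.0%). Then 25 / 0.85 = 29.4, rounded up to 30, which reproduces the enrolled number. The t-test alone does not give the intermediate 28; that is a separate matter. So the plan counts on about 30 × 0.85 = 25.5 men in the test.

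**2. Assumptions not in the documents.**
- Changes at 4 and 12 weeks are bivariate normal with SD 8 and correlation ρ = 0.5 to 0.8.
- The log-odds of being lost before week 12 rise by 1 to 2 for each SD of poorer 4-week change.
- Loss by week 12 is either the full 15% or less. The 28-to-30 margin is 2/30 = 6.7%; 5% is a further illustrative value.

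**3. Ceiling by formula.** If exactly the worst 15% at 4 weeks leave, the completers' mean shifts by 8 × ρ × φ(z)/0.85. With z = −1.036, φ(z)/0.85 = 0.274.
- ρ = 0.5: 8 × 0.5 × 0.274 = 1.10 points.
- ρ = 0.8: 8 × 0.8 × 0.274 = 1.76 points.

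Logistic selection is softer, so its shifts must be smaller.

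**4. Simulation** (n = 30, at least 20,000 trials per scenario):

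| Lost by week 12 | Completers' mean, true mean 5 | Two-sided error, true mean 0 |
|---|---|---|
| 5% | 5.2–5.5 | about 5–6% |
| 6.7% | 5.2–5.7 | about 5–7% |
| 15% | 5.5–6.3 | about 6–13% |

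The overstatement is 4–14% of the true mean at 5–6.7% loss (0.2/5 to 0.7/5) and 10–26% at 15% loss (0.5/5 to 1.3/5). The 13% error occurs only at ρ = 0.8 with slope 2; at ρ = 0.5 with slope 1 it is about 6%. The excess lies in the direction of benefit: at 15% loss that tail is 5–13% against a nominal 2.5%, while the other tail shrinks. With random drop-out the t-test is unbiased and has about 85% power.

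**5. Effect on a later trial's size.** At 15% loss the standardised change rises from 5/8 = 0.625 to about 0.71–0.85. Required n is proportional to 1/d², so a trial sized directly on the inflated value would enrol between (0.625/0.85)² = 0.54 and (0.625/0.71)² = 0.77 of the number needed. This is illustrative: a randomized trial would be sized on a between-group difference.

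**6. Using the 4-week values.** Two-visit likelihood estimate = completers' 12-week mean + b × (4-week mean of all men − 4-week mean of completers), where b is the completers' regression slope of 12-week on 4-week change. It gives about 5.0 throughout when drop-out depends on the 4-week value. If drop-out instead follows the unobserved 12-week response (15% loss, slopes 1–2), it gives 5.4–6.3 against 6.1–6.6 for completers. Under random drop-out its power is 86–89%.

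**7. Does significance survive at the planned effect?** Take 26 completers with mean 5 and SD 8: t = 5/(8/√26) = 3.19, p = 0.0038. Add 4 drop-outs.
- At zero change: mean 26 × 5/30 = 4.33, SD 7.63, t = 3.11, p = 0.0042.
- At 5 points worse: mean (130 − 20)/30 = 3.67, SD 8.19, t = 2.45, p = 0.021.

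**The case against.** Several stronger readings are tempting, and the documents do not support them.

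- **That the plan specifies a completers-only, visit-by-visit analysis.** It says neither. Both follow from the named tests plus silence on missing values.
- **That poor responders will leave.** The documents give no data on who drops out or why. Under random loss there is no bias.
- **That 15% will be missing at week 12.** Follow-up runs to 12 months and the timing of drop-out is not given. The 15% is applied to the sample size for the 12-week test, so full loss by then is an upper case rather than an impossible one.
- **That the p-value is always too favourable.** With weak selection (slope 0.5, ρ = 0.7, 15% lost) the mean rises to 5.4, but the median p is 0.0020 against 0.0017 with all 30 men, because the smaller n offsets the shift.
- **That a mixed model cures the problem.** Step 6 shows that it removes only part of the bias if drop-out follows the unobserved response. Men lost before week 4 have no follow-up value to contribute. The four-visit model with 30 men was not itself simulated.

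It can also be said that efficacy is secondary in an open-label safety pilot whose synopsis names only descriptive statistics, so that a stated missing-data rule and one sensitivity analysis would be enough. That limits the severity. It does not remove the case for using data already scheduled for collection, because the 12-week IPSS test sets the sample size and the results are meant to inform the next trial.

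**Conclusion.** The concern holds as a conditional one. The plan answers expected drop-out only with sample size, and its named tests leave recorded 4-week values unused for men missing at week 12. If poor early response raises the chance of leaving, a true 12-week reduction of 5 points would be reported as about 5.2–5.7 with 5–6.7% lost by then and 5.5–6.3 with 15% lost, and the SD would be too small. Two-sided error would be about 5–7% and 6–13%. These ranges rest on the assumed correlations and selection slopes, which the documents do not supply. At the planned effect the significance conclusion would probably stand, so the main harm is a biased estimate. This should be changed, but it does not undermine the pilot's safety objective.

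**What to change.** In Planned analysis of clinical endpoints:

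1. Estimate the 12-week IPSS change from a repeated-measures mixed model of change at 4 weeks, 12 weeks, 6 months and 12 months. Use visit as a factor, unstructured covariance with a simpler fallback stated in advance in case of non-convergence, and Kenward-Roger degrees of freedom. Include every treated man with a baseline and at least one follow-up value.
2. Use the same model for QoL bother, BPH impact index and Qmax. Keep the t-test and Wilcoxon test as supportive.
3. Add a sensitivity analysis over all treated men that sets drop-outs, including those lost before week 4, first to zero change and then to a worsening whose size is fixed in advance. Report the number missing at each visit.

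The cost is a few lines of text and modest programming, with no extra patients or visits. The downside is reliance on missing-at-random given the observed visits; if drop-out follows the unobserved 12-week response, only part of the bias is removed. The sensitivity analysis is there to show how much that could matter.
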